### **Research Design:**

This is a single center, exploratory, open-label, single-arm design study of 12 patients with BP. Treatment naïve and treatment refractory patients with BP will be treated with Taltz (Ixekizumab). Patients who are non-responders, to physician choice standard of care, will undergo a washout period and will be enrolled in the study. The washout period is 2 weeks for systemic non-immunosuppressive agents, topical steroids, and topical calcineurin inhibitors. A 4-week washout period will be used for systemic systemic immunosuppressive agents or 5 half-lives, whichever is longer, and no live vaccines should be administered within 12 weeks of the study drug. ([Table-1](#)) The study consists of 3 epochs: screening/washout period (of at least 1 week and up to 4 weeks), treatment epoch (of 12 weeks from screen/washout), and follow up epoch (of 6 weeks). The screening and washout period will allow for treatment naïve/ new diagnosis BP to undergo evaluation and diagnosis and for treatment refractory to undergo a washout. The total duration of the study will be 18 weeks.

The duration of treatment, 12 weeks, is based upon the maximal efficacy and dosing regimen of Taltz (Ixekizumab) in psoriasis.(7) Although psoriasis and BP are different disease processes, we would expect a response by 12 weeks of treatment. The open-label, single-arm design will allow for the assessment of the effects of Taltz (Ixekizumab) monotherapy in patients with acute and chronic disease in a relatively short time frame and will minimize study costs. This is critical as there may be a significant benefit either earlier or later in the disease course. This design will also allow for more patients to undergo targeted, serological analysis, which will provide in-vivo evidence of the pathogenesis of disease as well as the changes that occur during treatment. The open-label design of this study will have assessment bias on the part of the patient as well as the physician. The single-arm design will not allow for blinded assessment. In order to mitigate these issues, we will be using objective and validated methods of clinical assessment, which should be robust including: new blister formation, BPDAI, and prednisone usage. Additionally, the serological markers, which are secondary endpoints, will be assessed as an unbiased corollary to the primary effects of Taltz (Ixekizumab) on BP patients.

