BPDAI will be used for calculation of the overall disease activity in BP. The BPDAI is a standard, objective and subjective scoring system for cutaneous disease activity and pruritus respectively in BP. The pemphigus disease activity index (PDAI) has been validated in a different auto-immune blistering disease which shares some characteristics with BP. (23) Currently, the BPDAI is undergoing validation studies and it represents the most current method of objectively scoring BP. (24) The two BPDAI indices capture disease activity and quality of life. Additionally, current studies have found that the degree of cutaneous involvement at initial diagnosis, which would be captured by the BPDAI, is predictive of the likelihood of a subsequent flare. (25) Therefore, the data collected by the BPDAI is useful in the analysis of flares in the follow up phase. The BPDAI consists of scoring various types of lesions and creates a score out of 120 (see below left). A score of greater than 56, on the objective portion, has been considered severe disease. (24) Note that we will be using 5% body surface area (BSA) of disease or moderate to extensive disease (Moderate to extensive Bullous Pemphigoid defined by the mean number of new bullae and urticarial plaques that have appeared over the course of 3 days as determined by the investigator or referring physician (moderate disease defined by  $> 1$  and  $\leq 10$  new bullae and  $\geq 5$  urticarial plaques and extensive disease by  $>10$  new bullae)) as our initial criteria for enrollment in the study. In our clinical experience, 5% BSA represents a simple, clinical cutoff for disease requiring systemic agents. Formal BPDAI will not be conducted prior to enrollment.

BPD AI					
SKIN	ACTIVITY		ACTIVITY		DAMAGE
Anatomical location	Erosions/Blisters	Number of Lesions if <3	Urticaria/ Erythema / Other	Number of Lesions if <3	Pigmentation / Other
	0 absent		0 absent		Absent 0, present 1
	1 1-3 lesions, none > 1 cm diameter		1 1-3 lesions, none > 6 cm diameter		
	2 1-3 lesions, at least one > 1 cm diameter		2 1-3 lesions, at least one lesion > 6 cm diameter		
	3 >3 lesions, none > 2 cm diameter		3 >3 lesions, or at least one lesion > 10 cm diameter		
	5 >3 lesions, and at least one > 2 cm		5 >3 lesions and at least one lesion > 25 cm		
	10 >3 lesions, and at least one lesion > 5 cm diameter or entire area		10 >3 lesions and at least one lesion > 50 cm diameter or entire area		
Head					
Neck					
Chest					
Left arm					

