**C. How severe has your itching been in the past month?**

0 1 2 3 4 5 6 7 8 9 10  
None Severe

Score out of 10 =

Average INTENSITY SCORE FOR PAST MONTH = (A+B+C) = /30

OR

For BP patients with impaired mental functioning:

No evidence of itch (no excoriations)	0
Mild itch (isolated excoriations up to two body sites)	10
Moderate itch (excoriations on ≥ 3 body sites, impairment of daily activity)	20
Severe itch (generalized excoriation, sleep impairment)	30
TOTAL SCORE	/30

Adapted from: (6)

The subjective portion of the BPD AI is the pruritus component (see above right). This component is key to document as one of the major causes of morbidity in BP, in addition to the blistering, is the diffuse pruritus. Again, this test is undergoing validation currently and represents the most up to date measure for itch in BP.

Prednisone is the mainstay of therapy in BP and the dosage of prednisone correlates with disease activity. (11, 13, 18, 24) In this study, prednisone will be offered as a rescue therapy throughout the study (see [Supplemental 4](#)). This allows for examine the efficacy of Taltz (Ixekezumab) as a monotherapy, as well as its efficacy as a steroid-sparing agent. Oral corticosteroids will provide comfort, if needed, during the initiation phase of Taltz (Ixekezumab). All individuals on prednisone will be placed on Calcium 1200mg and Vitamin D 800IU.

ELISA Measurements for BPAG1 and 2 are the standard of care for diagnosis of BP. This test will be run centrally at the Mayo Medical Laboratory (MML) in Rochester Minnesota. The antibody levels, of BPAG2, correlate with disease activity. (26) Therefore, it is critical to monitor these antibody levels as this is a marker of disease severity and may be important in judging both a cutaneous and serological response to Taltz (Ixekezumab).

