#### **Supplemental 4: Corticosteroid Rescue**

Subjects will be evaluated at baseline and at 2 week follow ups for disease activity and severity. Those individuals scoring greater than 20 on the BPDAI pruritus component- VAS will be offered oral corticosteroids as follows:

- Corticosteroid Taper
  - Baseline
    - If BPDAI pruritus component- VAS greater than 20
      - Offer oral prednisone 20mg daily
      - If patient declines prednisone for any reason other than disease control this should be documented in the eCRF
  - At 2 week follow ups
    - If BPDAI pruritus component- VAS greater than 20
      - If prednisone naive
        - Offer to continue prednisone at 20mg daily
        - If patient declines prednisone for any reason other than disease control this should be documented in the eCRF
      - If currently on prednisone 20mg daily
        - Maintain on 20mg prednisone daily
        - If patient declines or decides to stop prednisone for any reason other than disease control this should be documented in the eCRF
      - If currently on 20mg prednisone every other day
        - Offer to increase prednisone at 20mg daily
        - If patient declines or decides to stop prednisone for any reason other than disease control this should be documented in the eCRF
    - If BPDAI pruritus component- VAS less than 20
      - If at 20mg daily
        - Taper prednisone to 20mg every other day

- If patient declines or decides to stop prednisone for any reason other than disease control this should be documented in the eCRF
  - If at tapered dose of 20mg every other day
    - Stop prednisone
    - If patient declines or decides to stop prednisone for any reason other than disease control this should be documented in the eCRF
- Calcium 1200mg and Vitamin D 800 IU will be prescribed along with oral corticosteroids and will be continued for the duration of the study once initiated

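### BPDAI and prednisone usage are offered as objective, validated safeguards against open-label bias, but the BPDAI is still under validation, directed prednisone follows an itch score, and the week 0–12 total can combine entry steroid with rescue

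*Combined protocol and SAP*

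**What the plan says.** The Research Design section concedes that an open-label, single-arm study carries assessment bias from both patient and physician. Its answer is: "we will be using objective and validated methods of clinical assessment, which should be robust including: new blister formation, BPDAI, and prednisone usage".

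Supplemental 1 describes the same instruments differently. On the index as a whole: "Currently, the BPDAI is undergoing validation studies and it represents the most current method of objectively scoring BP". On its two parts: "The BPDAI is a standard, objective and subjective scoring system for cutaneous disease activity and pruritus respectively in BP". On the itch form: "this test is undergoing validation currently and represents the most up to date measure for itch in BP". The index it does call validated is the pemphigus index, in a different blistering disease.

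Supplemental 4 sets the prednisone rule: "Those individuals scoring greater than 20 on the BPDAI pruritus component- VAS will be offered oral corticosteroids as follows". The later steps (maintain, increase, taper, stop) depend on whether the same score is above or below 20. The patient may also refuse: "If patient declines or decides to stop prednisone for any reason other than disease control this should be documented in the eCRF".

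Concomitant Medications and the Table-1 footnote allow a stable oral dose of up to 20 mg/day prednisone at entry. Secondary Outcome Measures and the Statistical Analysis Plan define the endpoint as the total prednisone dose over weeks 0–12. The Secondary Endpoints list in the Project Overview asks for the total in each epoch. The Introduction and Supplemental 1 give the purpose: prednisone use is to show how ixekizumab performs alone, "as well as its efficacy as a steroid-sparing agent".

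**The concern.** Two things are at issue.

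First, a measure offered as protection against unblinded reporting should not itself depend on that reporting. If a patient who knows the treatment expects benefit and reports less itch, the rule gives less prednisone. The prednisone total would then move in the same direction as the bias it is meant to counter. Calling the BPDAI validated also gives it a standing that Supplemental 1 does not.

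Second, a steroid-sparing statement needs to distinguish steroid the patient brought into the study from steroid the study had to add. One total over weeks 0–12 does not do that.

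What is at stake is interpretation. The sample size section says the data are for planning future studies. A planner who trusts the Research Design wording could read low prednisone use as objective support for the open-label blister result.

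**Working it through.** **Mitigation claim, checked against the rest of the protocol**

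- *Validated.* Research Design says yes for the BPDAI. Supplemental 1 says validation is in progress for the index and for its itch part.
- *Objective.* By Supplemental 1's own division, this fits the skin score. Pruritus is the subjective part.
- *Prednisone usage.* I went through each Supplemental 4 step: the baseline offer, the follow-up offer, maintain, increase, taper and stop. All use the pruritus score. None uses a blister count or the BPDAI skin score.
- *Who supplies the score.* Normally the patient does, on three 0–10 items (3 × 10 = 30 maximum). For patients with impaired mental functioning, an observer scores 0, 10, 20 or 30 from excoriations. That observer is also unblinded.

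**What the rule produces**

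Inputs from Supplemental 4 and Table-2: treatment visits every two weeks, giving six 14-day intervals in weeks 0–12 (84 days). Assumptions: every offer is accepted, and the taper applies to anyone at 20 mg daily, because Supplemental 4 makes no exception for entry steroid.

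- 20 mg daily for 14 days: 20 × 14 = 280 mg
- 20 mg every other day for 14 days: 20 × 7 = 140 mg

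For a prednisone-naive patient:

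- score never above 20: 0 mg
- score above 20 at baseline only, below 20 afterwards: 280 + 140 = 420 mg
- score above 20 at every visit: 6 × 280 = 1,680 mg

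A baseline score of 21 rather than 19, with scores below 20 afterwards, therefore means 420 mg rather than 0. This shows what drives the total. It does not estimate bias.

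**Whether the total separates entry steroid from rescue**

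The entry reference is the entry dose × 84 days.

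| Patient | Weeks 0–2 | Weeks 2–4 | Weeks 4–12 | Total | Entry reference | Change from entry |
|---|---|---|---|---|---|---|
| A: enters on 20 mg/day, itch always below 20 | 280 | 140 | 0 | 420 mg | 20 × 84 = 1,680 mg | 420 − 1,680 = −1,260 mg |
| B: naive, itch above 20 at baseline only | 280 | 140 | 0 | 420 mg | 0 mg | 420 − 0 = +420 mg |

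Patient A came off steroid and never met the rescue criterion. Patient B needed rescue. The endpoint as defined gives both 420 mg.

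**Entry doses the rule does not cover**

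The follow-up branches of Supplemental 4 are for prednisone-naive patients, 20 mg daily and 20 mg every other day. A permitted entry dose of 10 mg/day matches none of them. It has no taper step and no follow-up rescue step. If it were simply held (an assumption), it would add 10 × 84 = 840 mg to the total without any rescue.

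**The case against.** The best defence is that little is hidden. Research Design admits the bias, Supplemental 1 states the validation status and the subjective component, and Supplemental 4 publishes the itch trigger. Itch is a major source of morbidity in this disease, so itch-triggered rescue is clinically reasonable, and fixed doses limit physician discretion. Supplemental 1 also says that prednisone dose correlates with disease activity. All of this stands, but it does not make the mitigation sentence right: disclosure elsewhere contradicts the sentence and does not support it.

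A second defence is that the endpoint means rescue only. The Project Overview lists prednisone as rescue therapy, and the endpoint counts prednisone required. No sentence says entry steroid is counted, so the mixing is an inference. Against the rescue-only reading, no sentence excludes or subtracts entry steroid. The per-epoch wording also covers a screening/washout epoch, before Supplemental 4 first offers rescue at baseline. The fair charge is that the total, as written, can combine the two.

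Some stronger readings are tempting and are not supported:

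- *The total mainly reflects reported itch.* The documents do not say how often itch and blistering diverge, or how many patients will enter on prednisone.
- *An entry dose of 20 mg/day would run unchanged for 84 days and mimic untapered rescue at 1,680 mg.* Supplemental 4 tapers a patient at 20 mg daily once the score is below 20. If the score stays above 20, 20 mg daily is the rescue regimen itself. A line in Concomitant Medications discourages dose adjustments, but its scope is unclear and Supplemental 4 is the specific rule.
- *The primary endpoint is undermined.* New blisters are assessed separately, by examination and photography, and this point does not reach them.

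**Conclusion.** The point holds in limited form. The claim that the BPDAI is validated conflicts with Supplemental 1, and the claim that it is objective fits only its skin score. Prednisone usage does not belong among the safeguards against patient-side bias, because every directed step turns on an unblinded itch rating and then on the patient's acceptance. Separately, the week 0–12 total does not by itself support a steroid-sparing statement: two patients with opposite histories (−1,260 mg and +420 mg against entry) share the value 420 mg.

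That example assumes full acceptance of offers, the Supplemental 4 taper applied to entry steroid, and a total that counts all prednisone taken. The size of any bias cannot be derived from the documents. The endpoint is secondary and descriptive, in a 12-patient study meant for estimation only, so the consequence is for interpretation. No power or error-rate figure changes.

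**What to change.** 1. **Research Design.** Drop the word validated for the BPDAI, limit objective to its skin score, and remove prednisone usage from the measures said to mitigate bias.
2. **Secondary Outcome Measures and Statistical Analysis Plan.** For weeks 0–12, report entry-dose prednisone and itch-triggered rescue prednisone above the entry dose as separate amounts. Base any steroid-sparing statement on change from the entry dose and on rescue use, described as itch-triggered. Both are needed: a patient entering on 20 mg/day can show no rescue above entry, because the rescue regimen is also 20 mg daily, so only the change from entry is informative for that patient.
3. **Supplemental 4.** Add a branch for entry doses other than 20 mg daily or every other day, so that these patients have a defined rescue and taper step.

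The cost is wording in four places and a split of one descriptive summary for 12 patients. The entry dose must be known anyway to apply the 20 mg/day ceiling. No visit, procedure or sample-size change is needed. The downside is a more modest steroid-sparing statement.

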#### **Investigational and reference therapy:**

*Investigational:* Taltz (ixekizumab) 80mg subcutaneous (160mg week 0, then 80mg weeks 2, 4, 6, 8, 10, & 12)(7)

*Control (prior to washout):* Standard of care therapy prior to washout

*Rescue Therapy:* Prednisone (see [Supplement 4](#))

**Study design:** This is a single center, exploratory, open-label, single-arm design study of 12 patients. Treatment naïve and treatment refractory patients will be treated with Taltz (Ixekizumab). Patients who are non-responders, to physician choice standard of care, will undergo a washout period and will be enrolled in the study. The study consists of 3 epochs: screening/washout period (of at least 1 week and up to 4 weeks), treatment epoch (of 12 weeks from screen/washout), and follow up epoch (of 6 weeks). The screening and washout period will allow for treatment naïve/ new diagnosis BP to undergo evaluation and diagnosis and for treatment refractory to undergo a washout. The total duration of the study will be 18 weeks.

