The current therapeutic hierarchy, based upon randomized controlled trials (RCTs), for BP is largely reliant upon oral (up to 0.75mg/kg of prednisolone or prednisone) and topical (up to 40g of clobetasol daily) corticosteroids as well as adjuvant steroid sparing agents (azathioprine or mycophenolate mofetil). (11-14) A slow taper of oral corticosteroids is considered first-line for disease requiring systemic therapy. Therefore, the use of prednisone as a rescue therapy will allow for the assessment of Taltz (Ixekezumab) as a steroid sparing agent. Non-RCT based immunosuppression with rituximab and methotrexate have also been reported to be successful. (15, 16) Non-immunosuppressive agents including doxycycline, tetracycline, and niacinamide are reported to improve disease; however, only tetracycline and niacinamide have been compared to immunosuppressive agents. (17) There is one ongoing trial comparing doxycycline to prednisone in BP. (18)

Recently, IL-17 has been identified as a key driver of chronic inflammation in BP. (5) IL-17 inhibition may provide a much needed and more targeted treatment, with a better side effect profile. Taltz (ixekizumab) is a recombinant high-affinity fully human monoclonal antibody that targets IL-17A IgG1/kappa-class. Taltz (ixekizumab) neutralizes IL-17A and targets the Th17 pathway, which has been clearly shown to be involved in the pathogenesis of psoriasis with unprecedented responses. (7) In addition, the safety profile of Taltz (ixekizumab) is similar to that of etanercept with rare infectious complications. The clinical effects of targeting Th17 cells through IL-17A neutralization remain an unknown but attractive therapy in BP. The timing of targeting is paramount as prior studies in psoriasis often involve individuals with chronic plaque psoriasis in which there may be a larger percentage of Th17 cells. Therefore, the effects of Taltz (ixekizumab) in BP may be dependent upon the duration of disease prior to the institution of therapy.

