Our laboratory will perform a multiplex cytokine analysis on serum and blister fluid for Interleukin (IL)-6, -17, -22, -23 on an ELISA assay. Similar array based ELISAs will be used for Transforming Growth Factor beta (TGFb) and matrix-metalloprotease-9 (MMP-9) expression. The serum, cell pellet, and blister fluid will be stored per protocol and a single batch of samples from weeks 0, 4, 8, and 12 weeks will be run in parallel and in duplicate at the end of the study. The array-based kits are standardized and the dilutions of the serum and blister fluid will be optimized prior using the ELISA arrays. Additionally, we will perform analysis of RNA levels in the blister and serum. Finally, we will perform RNA analysis on archival biopsy tissue from each subject to correlate with the changes in the blood and serum.

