#### **Efficacy measures:**

- Cessation of new blisters.
- BPDAI (6)
- Total dose of prednisone required during phases of treatment
- anti-BP180 IgG and anti-BP230 IgG levels by ELISA
- Neutrophil and eosinophil counts
- IL-6, -17, -22, -23, TGFb, and MMP-9 levels in the serum and blister fluid

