The exploratory variables examined in this study will aim to correlate the clinical responses in BP patients with both systemic and local changes in the cytokine milieu. The Th17 inflammatory response is a key pathway in autoimmune, inflammatory diseases. (27) The most efficacious therapies in psoriasis target the Th17 pathway with IL-17 and IL-23 blockade. (28-30) The key cytokines in the Th17 pathway are IL-6, -17, -22, -23, and TGFb. These cytokines play a complex role in the pro- and anti-inflammatory response. (27) IL-6 is a pro-inflammatory cytokine that, when present with IL-23, leads to Th17 polarization. Th17 cells release IL-17 which produces a biological cascade of inflammatory molecules including: tumor necrosis factor alpha (TNFα),

IL-1 $\beta$ , GM-CSF, IL-6, IL-8, and MMP-9. (31) MMP-9 is elevated in blister fluid and serum of patients with BP and IL-17 is elevated in the blister fluid. (5, 32) Treatment with topical corticosteroids has been shown to decrease lesional MMP-9 and IL-17 levels, which correlated better with clinical improvement than did the BPAG1 and 2. (33) Therefore, following these IL-6, -17, -22, -23, TGF $\beta$ , and MMP-9 during therapy in treatment naïve and refractory disease may provide insight into the early and late pathogenesis in BP. Additionally, our findings may support the use of other serological biomarkers for monitoring disease activity as well as predicting therapeutic success in BP with the targeting of IL-17.

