TGF $\beta$  plays a particularly complex role in the pro- and anti-inflammatory response. TGF $\beta$ , when present in the absence of IL-6, -17, and -23, generates T-regulatory cells. The pathogenesis of T-regulatory cell generation and the resolution phase of inflammatory diseases have remained unclear; however, recent studies suggest that there may be a process of trans-differentiation of Th17 cells into T-regulatory cells. (34, 35) While the mechanism is still being deciphered, it appears that IL-17A receptor plays a key role in the formation of T-regulatory cells and it may be possible that IL-17A blockade is efficacious by not only down-regulating the Th17 response but by also up-regulating the T-regulatory response. A recent article in the journal, *Nature*, found that the Th17 cells themselves might be transdifferentiating into T-regulatory cells. (34) This has tremendous implications and may suggest the broad utility of IL-17A blockade in inflammatory diseases. However, more studies are needed to confirm these findings as well as the extent of plasticity of Th17 cells in inflammatory disease. If this current study is funded by Lilly, our group will be submitting for additional funding to examine the T-cell population during therapy to determine if the role that IL-17A blockade plays in T-regulatory cell formation and disease response.

In order to assess the inflammatory milieu of the blister and serum, a routine blood draw prior to drug therapy will be performed on the designated days and the serum will be stored for future use. The peripheral blood will be drawn and stored according to prior established protocols. Additionally, one active, tense blister will be drained using a needle and syringe. A minimum of 0.5cc of blister fluid and a maximum of 5cc of blister fluid will be stored via a simplified version of the serum protocol.

Our laboratory will perform a multiplex cytokine analysis on serum and blister fluid for Interleukin (IL)-6, -17, -22, -23 on an ELISA assay. Similar array based assays will be used for Transforming Growth Factor beta (TGF $\beta$ ) and matrix-metalloprotease-9 (MMP-9) expression. The serum and blister fluid will be stored per protocol and a single batch of samples at weeks 0, 4, 8, 12 will be run in parallel and in duplicate at the end of the study.

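### On-treatment IL-17 protein is confounded by the anti-IL-17A drug if the kit detects IL-17A, and should not count as an efficacy measure or disease-activity correlate unless tested for interference

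*Combined protocol and SAP*

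**What the plan says.** - **Assay.** Research Design plans "multiplex cytokine analysis on serum and blister fluid for Interleukin (IL)-6, -17, -22, -23 on an ELISA assay". All assays wait until the trial is over, when "a single batch of samples from weeks 0, 4, 8, and 12 weeks will be run in parallel and in duplicate". Optimising the dilutions is the only assay preparation described. Isoform, free or total format, and tolerance of the kit to drug are not mentioned.
- **Drug.** The Introduction describes ixekizumab as a "recombinant high-affinity fully human monoclonal antibody that targets IL-17A" and says that "Taltz (ixekizumab) neutralizes IL-17A and targets the Th17 pathway". Dosing is "160mg week 0, then 80mg weeks 2, 4, 6, 8, 10, & 12" (Investigational and reference therapy).
- **Timing.** Supplemental 1 says that "a routine blood draw prior to drug therapy will be performed on the designated days", and Safety Measures also puts blood draws before dosing.
- **Role.** The Efficacy measures list includes "IL-6, -17, -22, -23, TGFb, and MMP-9 levels in the serum and blister fluid". Supplemental 1 aims to correlate clinical responses with changes in the cytokines and says that "our findings may support the use of other serological biomarkers for monitoring disease activity as well as predicting therapeutic success in BP". The outcome list, however, puts the cytokines under Exploratory Outcome Measures, and the exploratory objective concerns predictors of response.
- **Other readouts.** Research Design and Supplemental 1 also plan RNA analysis in blood, blister fluid and archival tissue.

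**The concern.** The drug's target is also the analyte. Prior exposure to drugs against IL-17A or its receptor is an exclusion, so the week-0 sample is free of such a drug and every later one is not. The change from week 0 therefore carries whatever effect the drug has on the measurement itself.

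The direction depends on a kit property that the plan does not state. An assay whose antibodies compete with ixekizumab can read low because the epitope is occupied. An assay that does not compete reads free plus bound IL-17A, and may rise as complex accumulates even if production is unchanged. The same biology could look like a response with one kit and like pathway escape with another. Correlating either pattern with BPDAI or blistering would then say little about Th17 activity.

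Supplemental 1 draws support from a study in which topical corticosteroids lowered lesional IL-17 in line with clinical improvement. That precedent does not carry over directly, because there the treatment was not an antibody to the analyte.

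What is at stake is interpretation of the cytokine on which the trial's rationale rests, not the trial's main result.

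**Working it through.** The plan states no figure to reproduce, since it gives no drug level, IL-17 level or affinity. The check therefore counts the affected samples and then asks how large the distortion could be under stated assumptions.

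**1. Affected samples (from the documents).** 12 patients × 4 time points = 48 planned serum samples. 12 × 3 on-treatment time points = 36. The on-treatment draws are pre-dose, two weeks after the previous injection.

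**2. Trough drug level.** The doses are documented. Everything else is assumed: bioavailability F 0.4–0.9, volume V 3–10 L, half-life 5–20 days, antibody 150 kDa, one compartment, bolus approximation.

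Trough = Σ (dose × F / V) × 0.5^(days since dose / half-life)

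Lowest corner (F 0.4, V 10 L, half-life 5 days), week 4: 6.4 × 0.5^(28/5) + 3.2 × 0.5^(14/5) = 0.13 + 0.46 = 0.59 µg/mL. At weeks 8 and 12 the same corner gives 0.54 µg/mL, or 3.6 nM. The highest corner, at week 12, is 37.65 µg/mL, or 251 nM.

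**3. Molar ratio.** With a 32 kDa IL-17A dimer (assumed), 10 pg/mL is 0.00031 nM. At the lowest serum trough, drug exceeds IL-17 by about 11,400:1 at 10 pg/mL, 114:1 at 1,000 pg/mL and 11:1 at 10,000 pg/mL. If blister fluid holds only 10% of the serum drug level (assumed), these become about 1,140:1, 11:1 and 1.1:1.

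**4. Unbound fraction.** Molar excess does not settle this; affinity does. For 1:1 binding with total drug D and total IL-17A L:

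complex c = [(D + L + Kd) − √((D + L + Kd)² − 4DL)] / 2, and free fraction = (L − c) / L

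When D is much larger than L, this is close to Kd / (Kd + D).

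| Setting | Kd 0.001 nM | 0.01 nM | 0.1 nM | 1 nM |
|---|---|---|---|---|
| Lowest serum trough, D 3.58 nM, IL-17 10–10,000 pg/mL | 0.03% | 0.3% | 3% | 22–23% |
| Blister fluid at 10%, D 0.36 nM, IL-17 10–1,000 pg/mL | 0.3% | 3% | 22–23% | 74% |
| Blister fluid at 10%, IL-17 10,000 pg/mL | 2% | 11% | 38% | 78% |

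A lower drug level shows why the ratio alone misleads. At 0.1 µg/mL (0.68 nM at 146 kDa) and IL-17A at 100 pg/mL, the ratio is 219:1. Yet the free fraction is 0.1 / (0.1 + 0.68) ≈ 13% at Kd 0.1 nM and 1 / (1 + 0.68) ≈ 59% at 1 nM.

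**5. Total assay.** If production is constant, nearly all IL-17A is bound and steady state is reached, total IL-17A rises by the ratio of complex half-life to free half-life. With assumed values of 3–13 days and 1–24 hours, this is 72/24 = 3-fold to 312/1 = 312-fold. Partial binding would give a smaller rise.

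**The case against.** The strongest reply is that IL-17's role is modest. The outcome list ranks the cytokines as exploratory, the sentence about monitoring disease activity is hedged and covers a six-marker panel, and the Statistical Analysis Plan is descriptive and names no cytokine analysis. The sample size section says that the study serves estimation only. This stands, and it limits the weight of the point. It does not remove it, because the Efficacy measures list still includes IL-17 and Supplemental 1 still plans the correlation with clinical response.

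A reader might also count IL-17 among the secondary serological markers that Research Design offers as a counterweight to open-label bias. The documents do not clearly support that. The secondary serological outcomes actually listed are the anti-BP180 and anti-BP230 levels and the cell counts.

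A second reply is that the kit is unspecified. An assay for a form that the drug does not bind would be unaffected, and a validated drug-tolerant assay could show target engagement. This also stands, and is the reason to test before deciding.

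Third, the planned RNA analysis already gives a readout that an antibody to the protein does not bind. That is a real mitigation, although the plan does not make it a substitute for on-treatment IL-17 protein.

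**Conclusion.** The concern holds in a limited form. If the kit detects IL-17A, the on-treatment change from week 0 is confounded by drug binding at three of four time points, and the plan contains nothing to detect or allow for this. Week-0 IL-17 remains usable as a predictor of response.

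A reader might infer that nearly all IL-17A is drug-bound in every on-treatment sample, so that these values can never be used. The documents do not support that. The Introduction gives high affinity only as a description, without a value. Under the assumed ranges, the unbound share at the lowest modelled trough runs from 0.03% in serum to about 78% in poorly penetrated blister fluid. Partial binding still confounds the change, but by an unknown amount. Slow clearance of the complex, and hence a rise in a total assay, is likewise an assumption.

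The primary endpoint, BPDAI, prednisone use and safety are unaffected. The change should be made before the batch is run, but it does not threaten the main result.

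**What to change.** 1. **Test first.** In the assay optimisation already planned under Research Design, spike ixekizumab into pooled week-0 serum and pooled week-0 blister fluid containing known IL-17A. The spike range should cover the plausible troughs; on the assumptions above that is about 0.05 µg/mL (10% of 0.54) to 38 µg/mL. Record the isoform detected and whether the kit reads free or total IL-17A.
2. **Relabel.** In Efficacy measures, Exploratory Outcome Measures and Supplemental 1, keep week-0 IL-17 as a predictor of response. Label on-treatment IL-17 protein as pharmacodynamic, and report it as free, total or not interpretable, as the spike test shows. Do not use it as an efficacy measure or disease-activity correlate unless the test shows no interference.
3. **Use the other readouts.** Judge on-treatment pathway effect on IL-6, IL-22, IL-23, MMP-9 and RNA, all already planned and none bound by the drug.

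The cost is a few extra assay wells, a small amount of pooled week-0 material and wording changes in three places. Because samples are stored and run together at the end, no visit or patient procedure changes. The downside is that the on-treatment IL-17 trend may be lost as an efficacy readout.
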